Main study endpoints: The main study outcome comprehends the psychometric properties of the PROM for symptom assessment of OAB symptoms. Secondary outcomes are increase in ESM score for OAB symptoms and environmental and psychosocial factors (*e.g.* as measured by the PROM) from one time point (t-1) to the next (t).

Burden, risks and benefits: The burden that is associated with participation in this study comprises completing the PROM questionnaire several times a day, which interrupts daily life due to its random character. Furthermore, the burden is limited to completing a SR-BD and other symptom questionnaires. Most importantly, participating does not bring along

important health related risks. However, awareness could trigger symptoms and therefore be considered as a burden. Nevertheless, for the patients it could be beneficial too to know what triggers complaints, to cope better with their disease.

INTRODUCTION AND RATIONALE

The overactive bladder syndrome (OAB) is defined by the International Continence Society (ICS) as a symptom complex of urgency, usually with frequency and nocturia (awakening at night to void), with (OAB wet) or without (OAB dry) urinary urgency incontinence. Urgency is the complaint of a sudden compelling desire to pass urine, which is difficult to defer⁵. OAB is clinically diagnosed using the ICS criteria of \geq 8 micturitions and at least 1 urgency episode per 24 hours.

It is estimated that approximately 16-17% of the adult population of the Western world is affected by OAB ^{6,7}. The incidence of OAB, both wet and dry increases by age ⁸⁻¹⁰, and because of the worldwide ageing of the population, the number of adults affected by urinary urgency incontinence (UUI) would increase ¹¹. The health care costs of OAB are high ¹², and work productivity can be significantly impacted as well ¹³. In addition, OAB can be associated with comorbidity and increased mortality^{14,15}. Furthermore, OAB with and without incontinence has been associated with significantly lower quality of life scores compared to matched controls without voiding complaints⁸. It is of particular interest that OAB does not only affect the patients, but also has an impact on family members ¹⁰.

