ESM has proven to be a viable and novel approach to assess symptoms, affective states and contextual factors at the level of the individual subject²⁷. It provides precise, prospective information that may contribute to clinical practice²⁶ with several distinct advantages over traditionally used (retrospective) assessment of mental health related phenomena²⁸. OAB shows fluctuating symptom patterns in which urological complaints might be influenced by daily life factors as well as psychological and psychiatric comorbidities. To our knowledge, there are no previous studies on the use of ESM in a urological patient population. In order to study the performance of ESM in a population as such there is a need for developing a patient-reported outcome measure suitable for real-time symptom assessment of urological symptoms, using the ESM principle. Patient-reported outcome measures (PROMs) are assessment methods completed by patients, and are meant to capture one or several aspects of a disease course or health status²⁹. Focus group research in OAB patients was done for item selection and to evaluate the quality of the PROMs according to the ESM principle. The outcomes of the focus groups have been discussed in an expert meeting and a final questionnaire has been constructed, specifically for the ESM in the urological patient population. Now, this OAB-specific ESM tool should be tested to see if there is a difference between symptom scores on ESM and the currently used retrospective reports and SR-BDs. Furthermore content validity, reliability and the accuracy will be tested to validate the developed ePRO in OAB patients. Additionally, specific triggers for the onset of OAB complaints will be objectified, with use of the OAB specific ESM tool. It will be objectified if there is a direct link between OAB and psychiatric disorders as depression, anxiety and stress too.

Summarizing, electronic, repeated symptom assessments during daily activities should assure ecological validity and eliminate recall bias, lead to higher compliance rates, and capture symptom variability during the day. For these reasons it is expected that the Experience Sampling Method (ESM) may prove to be a more objective tool for evaluation and quantification of urgency and other urological complaints that will overcome the limitations of currently used retrospective symptom assessment methods in OAB.

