Primary aim: To validate and test the reliability of electronic patient-reported outcome (ePRO) for the evaluation of the complex symptoms and their potential triggers in OAB patients in day-to-day life with the use of the Experience Sampling Method.

Objectives:

1. To assess content validity of the developed ePRO.

Hypothesis: We consider content validity of the ePRO adequate since items were carefully selected based on evidence from qualitative studies. Furthermore, item relevance was judged by a multidisciplinary panel of experts in the fields of urology, gastro-enterology, psychiatry and gynaecology as well as by OAB patients.

2. To assess concurrent validity of the developed ePRO.

Hypothesis: We hypothesize to find good correlations between ESM scores (*i.e.* the newly developed ePRO) and 'concurrent' instruments (*i.e.* conventional retrospective questionnaires), since we purport to measure the same constructs with both methods. However, ESM measures real-time symptoms whereas our conventional questionnaires measure retrospectively. Therefore, we do not expect to find perfect correlation coefficients, *i.e.* >0.8. Correlation coefficients between 0.4 and 0.8 are considered appropriate. Correlation coefficients lower than 0.4 reflect very weak or no correlation between the methods, which probably means that we are measuring some other construct with our new ePRO than is measured with the conventional method (current 'gold standard'). On the contrary, correlation coefficients higher than 0.8 reflect very strong correlations, meaning that we are more or less measuring exactly the same construct. In this case, there is no rational for replacing the conventional methods by the new (more intensive) method. For each correlation coefficient its significance will be checked as well.

3. To assess internal consistency of the developed ePRO.

Hypothesis: We hypothesize that internal consistency of the ePRO will be moderate to good, since items were based on theoretical constructs as described in literature. Therefore, we expect to find correlation coefficients (Cronbach's α) of >0.6.

4. To assess test-retest reliability of the developed ePRO.

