3. STUDY POPULATION

3.1 Population

Thirty-three male and thirty-three female OAB patients will be recruited at the outpatient Pelvic Care Centre in Maastricht UMC+ the outpatient clinic Urology at Zuyderland Heerlen/Sittard and the outpatient clinic Urology at University Hospital Antwerp. Patients will be diagnosed with OAB by their urologist using the ICS criteria for OAB⁵.

Furthermore, thirty-five male and thirty-five female healthy volunteers will be included in order to exploratively evaluate the ability of ESM to discriminate between OAB patients and healthy controls, in terms of triggers for the occurrence and/or persistence of urological symptoms. This control group will be sex- and age-matched to the group of OAB patients.

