4.1.2 Part II Validation

Main study parameter/endpoint

- Urgency scores as measured by two self-report measures:
 - The ESM tool (*i.e.* momentary measurement)
 - The sensation-related bladder diary (*i.e.* retrospective measurement with a recall period of several minutes)

Secondary study parameters/endpoints (if applicable)

- Symptom scores (other than urgency) as measured using the ESM tool:
 - Micturition habits, *i.e.* number of micturitions each day and the force of the urinary stream using the Visual Prostate Symptom Score (VPSS) (see Figure 2).
 - Gastrointestinal symptoms
 - Psychological symptoms
 - Gynaecological symptoms
 - Extra-intestinal somatic symptoms

- Data on context and environment at each time an ESM questionnaire is completed
- Symptom scores (other than urgency) as measured using the sensationrelated bladder diary:
 - Micturition habits, *i.e.* number of micturitions each day
- Symptom scores (other than urgency) as measured using the single-time retrospective questionnaires:
 - Urological symptoms:
 - Female participants: OABq, ICIQ-FLUTS, 3IQ
 - Male participants: OABq, ICIQ-MLUTS, 3 IQ, IPSS, IIEF-5
 - Psychological symptoms: HADS
 - Gynaecological symptoms : Questionnaire Werkgroep Bekkenbodem NVOG
 - Extra-intestinal symptoms and Quality of Life scores: SF-36

Figure 2. The Visual Prostate Symptom Score.

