4.2 Study procedures

Participants will accomplish the Experience Sampling Method for seven consecutive days during their regular daily life. Previous ESM validation studies validated for the use of the ESM for seven days too.⁴³

During the last three consecutive days of the ESM, patients will also keep a SR-BD following the standard of care. A 7-day voiding diary is a reliable and valid method for documenting the change in symptoms of overactive bladder in men and women with predominantly urge incontinence. However, 3-day voiding diaries are as accurate as the 7-day diary, but patient burden is reduced. Therefore, a 3-day sensation-related bladder diary is used in the standard of care of the department of Urology of MUMC+, Zuyderland Heerlen/Sittard and University Hospital Antwerp.^{46,47} Furthermore, during the first four days of the study, ESM outcomes are not influenced by outcomes reported with the sensation-related bladder diaries. This is in alignment with previous studies.^{4,43}

On the last day of the study period, participants will fill out the several retrospective symptom questionnaires.

To accomplish the ESM, they need to carry their own smartphone or (in case they do not have one) another digital device, which will be lent to them for this period. On the smartphone or digital device an application, specifically developed for this project, will be downloaded. This application will run the PROM as follows.

The concerning device will send out an auditory signal 10 times a day at random moments between 07:00 am and 22:00 pm. During 10 minutes following the signal participants can complete a questionnaire, *i.e.* the developed PROM, on the device (see F1. 'ESM_Vragenlijst_Versie 1.0 (11.08.2017)'). After these 10 minutes the questionnaire will not be available until the next beep and is considered missing data. Therefore, subjects are instructed to complete as many questionnaires as possible each day, as soon as possible following each beep, but to pass over questionnaires when completing is impossible. For example, subjects should not fill out questions when driving a car. The questions will be identical between the different moments during the day.

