Additionally, participants will be instructed to complete a different ESM questionnaire in the morning when they wake up (see F1. 'ESM_Ochtend Vragenlijst_Versie 1.0 (11.08.2017)'). A timeline portraying which questionnaire has to be filled out at what time during the study period is reported in figure 2.

4.2.1 **PROM** development

The process of question selection for the development of an OAB specific ESM tool is a crucial step since content, construct and criterion validity are dependent on these questions. The questions that will be used were derived from previously published ESM studies and currently used OAB symptom questionnaires and further selection took place based on patients input during focus group interviews. Following, the items were evaluated by a multidisciplinary expert group consisting of highly esteemed and experienced investigators in the fields of urology, gastroenterology, psychiatry and gynaecology. Herewith, the number of items was further reduced in order to minimize the burden associated with completing the questionnaire at regular intervals.

This stepwise approach was performed according to guidelines for symptom assessment tool development.

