4.2.2 Tool development

To apply ESM as a symptom assessment method in this study, an application suitable for smartphones has been developed. This application runs the previously selected set of items, as described in section 5.2.1.1. 'PROM development'.

The application can be downloaded freely on the personal smartphone of each participating subject. Once the application is downloaded and activated, it will work both online and offline to ensure that no assessments will be missed when not connected to the Internet. In online situations the answers will be directly and automatically sent to the general database; when offline the answers will be temporary stored at the smartphone and will be sent to the database as soon as an Internet connection is available. Encryption of data to assure on patient's privacy is described in detail in section 9.1 'Handling and storage of data and documents'.

Questions in the application will be designed in a hierarchical order, *i.e.* if the patient has no symptoms at that particular moment, there is no rationale for assessing triggers and therefore these questions will be automatically set to a default of "no" or "none". Further, if patients find an auditory signal

disturbing during their daily activities, they will be able to choose a vibration signal instead.

- 4.2.3 Retrospective symptom assessment conventional questionnaires Apart from ESM, participants will be instructed to complete a SR-BD during last 3 consecutive days of filling out the ESM (see 'F2. ESM_sensationrelated bladder diary_Versie 1.0 (11.08.2017)'). The SR-BD has to be filled out after each micturition. This is a voiding diary where people fill out at what time they had to void, how high the voided volume was and how high the urgency and perception of bladder fullness was what they experienced. Furthermore they have to fill out if and how much urine loss they had. Furthermore, participants will be instructed to complete additional (singletime) retrospective questionnaires, at the end of the test period of 7 days:
 - Baseline questionnaire for demographic characteristics (see F1.
 'ESM_Algemene Vragenlijst_Versie 1.0 (11.08.2017)').

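### Trigger items skipped at symptom-free beeps and stored as no or none cannot show what triggers the onset or occurrence of OAB symptoms

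*Combined protocol and SAP*

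**What the plan says.** The app's questions are hierarchical. Under 4.2.2, without symptoms at a given beep "there is no rationale for assessing triggers and therefore these questions will be automatically set to a default of" *no* or *none*. The question is not shown, but a substantive answer is stored.

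The trigger aims appear in three places:

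- Introduction and rationale: with the ESM tool, "specific triggers for the onset of OAB complaints will be objectified".
- Section 3.1: healthy volunteers are included to explore discrimination between patients and controls "in terms of triggers for the occurrence and/or persistence of urological symptoms".
- Section 1, Part II primary aim: the ePRO serves the "evaluation of the complex symptoms and their potential triggers in OAB patients in day-to-day life".

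The Summary adds a lagged outcome: "Secondary outcomes are increase in ESM score for OAB symptoms and environmental and psychosocial factors", from one time point (t-1) to the next (t). Section 4.1.2 lists "Data on context and environment at each time an ESM questionnaire is completed", which suggests that at least these items are asked whether or not symptoms are present.

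The missing-data rules concern questionnaires that were not completed (4.2 and 6.1). Section 6 rules out imputation. None of these covers a question skipped inside a completed questionnaire. Section 6 names no model for triggers.

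**The concern.** To call an exposure a trigger, one must know how often it is present when no symptom follows, as well as when one does. Symptom-free beeps supply that comparison, and the filter stops the question from being asked there. Because the skipped answer is stored as *no* or *none*, an analyst cannot tell it from a real negative, and nothing in the plan prevents its use as data.

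Two stated aims are at stake where they rely on filtered items: identifying triggers of onset, and the occurrence part of the patient-control comparison. False zeros can be recoded later if the symptom score that drives the filter is stored. An exposure that was never asked about cannot be recovered.

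**Working it through.** The plan gives no figure on this point to reproduce. From the documents come the filter rule (4.2.2), the onset and occurrence aims (Introduction, 3.1), the t-1 to t structure (Summary) and 10 beeps a day for 7 days (4.2). All rates below are assumed. Objective 5 in Section 1 says only that OAB-like symptoms often occur in healthy subjects, so a range is used for controls.

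**Step 1: the beep before onset.** Let T be true exposure (0/1), S symptoms (0/1) and R = T × S the stored value. Onset at t requires S = 0 at t-1, so R at t-1 is always 0. It has no variance, and no lagged onset effect can be estimated.

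**Step 2: the same beep.** R = 1 is impossible when S = 0, so the exposed, symptom-free cell is always 0. The odds ratio is infinite whatever the truth.

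**Step 3: check by simulation.** 50 subjects × 7 days × 10 beeps, 5 replicates; onset risk 20% if unexposed, chance that a symptom persists 50%, symptom at the first beep 30%, exposure 10%, 30% or 50%, true onset odds ratio 1, 2 or 3 (nine scenarios).

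- Items asked at every beep: estimated odds ratios were 0.98–1.02, 1.84–2.04 and 2.74–3.03 for true values 1, 2 and 3.
- Filtered items: not estimable in any scenario. At odds ratio 2 and 30% exposure, the onset table had 8,221 and 2,557 in the unexposed row (no onset, onset) and 0 and 0 in the exposed row.
- Same-beep table with no effect and 30% exposure: 12,443 and 3,538 unexposed (symptom-free, symptomatic), 0 and 1,519 exposed. The unfiltered odds ratio was 1.01.

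**Step 4: false zeros, if the item records exposure.** With exposure p = 0.30 in both groups, no effect and symptom rate q, the stored rate is p × q. For OAB at q = 0.40 it is 0.30 × 0.40 = 12%.

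| Control symptom rate | Stored rate in controls | False OAB-to-healthy ratio |
|---|---|---|
| 30% | 9% | 12/9 = 1.3 |
| 20% | 6% | 12/6 = 2.0 |
| 10% | 3% | 12/3 = 4.0 |

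**Step 5: restricting to symptomatic beeps.** Let q0 be the symptom rate without exposure and q1 the rate with it. Then P(trigger | symptom) = p·q1 / [p·q1 + (1−p)·q0].

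- Common odds ratio (OR) of 3, with q1 = OR·q0/(1−q0+OR·q0): q1 = 0.667, 0.563, 0.429 and 0.250 at q0 = 0.40, 0.30, 0.20 and 0.10. The restricted rate is 41.7%, 44.6%, 47.9% and 51.7%, so it varies with the baseline rate although exposure and odds ratio are equal.
- Common risk ratio (RR): q1 = RR·q0, q0 cancels, and the result is p·RR/(p·RR + 1 − p). With RR = 1.5 it is 0.45/(0.45 + 0.70) = 39.1% at every baseline rate.
- No effect: 30% in both groups.

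**Step 6: other item wordings.** If the item asks what caused the present symptom, *none* is a fair answer without symptoms and Step 4 does not apply; the item gives attribution at symptomatic beeps only. If it looks back over the time before the beep, it may capture some pre-onset exposure at the first symptomatic beep, but there is still no symptom-free beep to compare it with.

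**The case against.** The strongest reply is that the onset aim may rest on items outside the filter. The Summary frames the t-1 to t outcome around environmental and psychosocial factors, and 4.1.2 has context and environment recorded at each completed questionnaire. This stands, and it limits the point to filtered items. The item wording is in an annex cited in 4.2 that is not in the public documents, so which items are filtered, and which symptoms open the filter, may be settled there.

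It is also fair that filtered items may ask for a perceived cause, so that skipping them is sensible. Then *none* is not a false zero, but attribution at symptomatic beeps still does not establish a trigger of onset. The 3.1 comparison is exploratory and also names persistence, which the filter does not block. Section 6 has no trigger model, so no specified analysis is damaged.

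Three stronger readings are tempting and not supported:

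- A reader might infer a contradiction with 4.2, where "The questions will be identical between the different moments during the day". An identical form can still branch.
- A reader might count every symptom-free beep as lost exposure. For a perceived-cause item there is no exposure to lose there.
- A reader might infer that comparing groups within symptomatic beeps is always biased. Step 5 shows that this depends on the effect scale, and the documents fix none.

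**Conclusion.** The point holds for items behind the symptom filter. They have no observed symptom-free comparison, so they cannot support the onset aim or the occurrence part of the patient-control aim. That conclusion follows from the rule in 4.2.2 and needs no assumed rates. The false ratios of 1.3 to 4.0 do rest on assumptions: exposure-type items, 30% exposure, no effect, and the symptom rates shown.

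It would go too far to infer that the trigger aims as a whole fail. Items asked at every beep, severity or persistence analyses within symptomatic beeps, and the urgency comparison between ESM and the bladder diary are untouched. The matter should be fixed, but it does not threaten the main comparison.

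**What to change.** 1. In 4.2.2, replace the default with a distinct code for a question not asked, and extend the missing-value rule in 6.1 to it. If data are already collected, recode from the stored symptom score that drives the filter.
2. State, or cite from the annex, which items are filtered, which symptoms open the filter, and whether each item records exposure or asks for a perceived cause.
3. Base onset and occurrence analyses, including t-1 to t analyses that start from a symptom-free beep, only on items asked at every beep. Use filtered items only within symptomatic beeps, for severity, persistence or perceived cause.
4. Report any OAB-versus-healthy comparison of filtered items as descriptive, noting that P(trigger | symptom) varies with the baseline symptom rate under a common odds ratio but not under a common risk ratio.
5. Optional: ask exposure-type trigger items at every beep.

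The first four cost almost nothing and add no participant burden, but recoding does not recover exposure that was never asked about. The fifth adds a few questions at symptom-free beeps, which has to be weighed against 4.2.1, where "the number of items was further reduced in order to minimize the burden"; it must be in place before data collection to be of use.

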4.3 Withdrawal of individual subjects

Subjects can leave the study at any time for any reason if they wish to do so without any consequences. The investigator can decide to withdraw a subject from the study for urgent medical reasons.

4.4 Replacement of individual subjects after withdrawal

We do not expect many dropouts, because the study is not very burdensome in a physical way and so, is not very difficult to complete. However, accomplishing ESM for 7 days is quite time-consuming and might intervene with daily activities, so possibly, not all subjects will be perfectly compliant to the method (i.e. completing the PROM at 10 random moments during 7 consecutive days). In case a subject decides to end participation before the 7-day participation period is completed, this subject will be considered a drop-out. Data can still be used in the comparison of assessment methods (part I), to determine the test-retest reliability and to assess the accuracy of the discriminatory model using a confusion matrix.

